Upon resolution of acute illnesses including diarrhoea, pneumonia, gross electrolyte imbalance, or septicemia, severely malnourished children aged 6 months to 5 years will be randomized to receive any of the three treatment regimens:

1. Home-based nutritional rehabilitation with home follow-up (treatment A, n=75)
2. Home-based nutritional rehabilitation with outpatient follow-up (treatment B, n=75)
3. Hospital-based nutritional rehabilitation (treatment C, n=75).

Children on treatments A and B will stay in the NRU of the CRSC for a period of 7 days, during which their condition will stabilise and their mothers will have learnt the preparation of *khichuri* and *halwa*, which are low-cost, nutritious diets being successfully used in the CRSC. Following discharge after 7 days, these children will continue to be fed *khichuri* and *halwa* prepared by the mothers at home. Children on treatment A will be visited at home for follow-up by health workers at regular intervals during which growth will be monitored, micronutrients supplied, and morbidity recorded. This will continue until the children achieve an oedema-free weight-for-height (WH) >80%. Children on treatment B will be required to attend the outpatient follow-up clinic until they achieve oedema-free WH >80%. Children on treatment C will remain in the NRU and fed *khichuri* and *halwa* according to a standardized dietary schedule until achievement of a WH >80%. Outcome measures that will be used in comparing the three treatments will include growth, time to recovery (achievement of oedema-free WH >80%), rate of weight gain in g/kg per day calculated from lowest weight to discharge weight, speed of loss of oedema, failure to respond, morbidity (number and duration of episodes over equal periods of follow-up for both groups), mortality, and cost of treatment.

KEY PERSONNEL (List names of all investigators including PI and their respective specialties)

Name	Professional Discipline/Specialty	Role in the project
1. [name]	Paediatrician & Nutritionist	P.I.
2. [name]	Internist	Co-investigator
3. [name]	Paediatric Gastroenterologist & Nutritionist	Co-investigator
4. Medical Officer (to be named)	Physician	Co-investigator
5. [name] *	Nutritionist	Collaborating investigator

\* Reader in Community Nutrition  
London School of Hygiene & Tropical Medicine

Principal and co-investigators are from the Clinical Sciences Division, ICDDR,B.

## • DESCRIPTION OF THE RESEARCH PROJECT

---

Concisely list in order, in the space provided, the hypothesis to be tested and the Specific Aims of the proposed study. Provide the scientific basis of the hypothesis, critically examining the observations leading to the formulation of the hypothesis.

---

### **Hypothesis to be tested:**

1. After an initial period of hospitalization, severely malnourished children recovering from diarrhoea can be managed at home using indigenous, low-cost, and culturally acceptable diets.
2. The cost-benefit of a home-based programme for nutritional rehabilitation of severely malnourished children recovering from diarrhoea will be more than the conventional hospital-based programme.

### **Specific Aims:**

---

Describe the specific aims of the proposed study. State the specific parameters, biological functions/ rates/ processes that will be assessed by specific methods (TYPE WITHIN LIMITS).

---

1. To plan, organize and establish an effective home-based programme for rehabilitation of severely malnourished children recovering from diarrhoea.
2. To compare by means of a prospective, randomised study, the outcome, including growth, rate of weight gain, speed of loss of oedema, days to achieve oedema-free weight-for-height (WH) 80% of National Centre for Health Statistics (NCHS) median reference, failure to respond to nutritional therapy, morbidity, mortality, and cost of treatment of children managed by home-based nutritional rehabilitation (with follow-up at outpatient clinic or at home) with those managed in the conventional hospital-based programme (definition of failure to respond and morbid conditions are detailed in the *methods* section).

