**Anti-helminthic treatment:** Children >1 year of age will be given mebendazole, 100 mg two times daily for 3 days, if such treatment has not been provided in the last six months. This treatment will be provided after two weeks of nutritional rehabilitation.

**Follow-up:** After the child is discharged from the NRU, a health worker will visit the child every week for one month and then at fortnightly intervals until the child achieves an oedema-free WH >80%. During each visit, the child's general condition will be assessed, weight and height (or length) measured, presence or absence of oedema noted, supplies of micronutrients provided, compliance of feeding and micronutrient supplementation checked by 24 hours recall, and morbidity recorded, if any. To aid recall of morbid conditions, on each visit mothers will be given a pictorial calendar portraying a well child and children with diarrhoea, vomiting, cough, fever, eye infection, or discharging ears [10]. Mothers will be requested to record daily on the calendar whether the condition had been present or absent in the previous 24 hours. Morbidity will then be recorded on a precoded form with the help of the calendar. Diarrhoea will be defined as the passage of three or more watery or liquid stools per day. An episode will be considered new if at least two diarrhoea-free days intervene between the present and previous episodes. The health worker's identification of children with pneumonia of different grades of severity will be based upon WHO guidelines [11]. Lack of weight gain for two consecutive visits will constitute failure to respond. The health worker will refer to the CRSC any child with suspected serious illness, i.e., diarrhoea with some or severe dehydration, pneumonia, ear or throat infection, repeated episodes of fever, loss of appetite, or failure to respond to feeding. Self referral will also be encouraged and entertained at any hour of the day. The child will be evaluated and managed accordingly by any of the investigators (during day time) or the on-duty physician (at night). Readmission to the hospital and the NRU will depend upon existing CRSC guidelines. Any child readmitted to the NRU will not be re-enrolled into the study, but will maintain the pre-readmission status as a study subject. The physician will also record in the precoded form diagnosis, treatment, duration, and outcome of any severe illness including relapse of severe malnutrition or septicemia.

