### **Treatment B**

Children on treatment B will also stay in the NRU for a stabilisation period of 7 days during which their mothers or caretakers will have learnt preparation of khichuri and halwa and taking care of the children at home. Dietary therapy, micronutrient supplementation, training of mothers or caretakers, immunization, and anti-helminthic treatment will be the same as in treatment A. Thereafter, they will be discharged and advised to attend the NFU every week for one month and then at fortnightly intervals until they achieve an oedema-free WH >80%. If a child develops an acute illness or the general condition is not satisfactory at the time of discharge, then the discharge will be postponed till resolution of the illness. The protocol for follow-up will be the same as in treatment A, the difference being that the children will be

brought to the NFU by the parents. If a child fails to attend the NFU within 2 days of a specified follow-up day, a health worker will make a home visit, do the follow-up and reiterate the importance of bringing the child to the NFU for follow-up. The health worker, in course of her follow-up, will try to find out the reason(s) for defaulting. A previous study conducted at the NRU [12] to find out the cause of defaulting showed the principal reason to be the wrong perception of the parents that follow-up was not needed since the child was okay. Other reasons that came up during the previous study, and that will also be inquired during the follow-up visit by the health worker in this study, include: inability of the mother to come to the hospital alone, illness of the mother or child, distance, visit to village homestead, inability to leave other children at home alone, inability to afford the travel expenses, and death of the child.

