### **Treatment C**

Children on treatment C will remain admitted in the NRU until they have achieved an oedema-free WH >80%, and have a good general condition. This will typically involve a stay in the NRU for 15-25 days. The standardized feeding schedule will be followed and micronutrient supplements provided until discharge (refer to treatment A). Training of mothers or caretakers, immunization, and anti-helminthic therapy will be the same as in treatment A, except that in this treatment schedule the mothers or caretakers will receive more educational lessons due to their longer stay in the NRU. Morbid conditions occurring during rehabilitation, including diarrhoea, pneumonia, or septicemia will be recorded in precoded forms. After being discharged from the NRU, the children in this group will be advised to attend the NFU at intervals of two weeks for one month, and then at monthly intervals until they achieve a WH >90%. The entire family will be encouraged to come for the follow-up visit during which preparation of khichuri and halwa will be demonstrated to the mothers and then served to all members. Health education of the mothers or caretakers will be reinforced. Iron supplementation will be continued for 2 months in usual doses. Intercurrent illnesses such as diarrhoea or pneumonia will be treated.

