### **Sample Size**

A preliminary analysis of 51 severely malnourished children (WH <70%) who received nutritional rehabilitation in our NRU after recovering from diarrhoea showed that the weight gain was  $8.4 \pm 7.3$  g/kg.day, and the time to achieve WH >80% was  $22.5 \pm 6.2$  days. In designing a trial with three or more groups, it is suggested that pair-wise comparisons between groups of central interest be first decided upon [13]. It is assumed that the proposed method of home-based nutritional rehabilitation with outpatient follow-up will result in a relatively lesser weight gain of 4 g/kg per day, will require approximately 35 days to achieve WH >80%, and lead to a 35% reduction in cost of treatment. Sample sizes of 58, 15, and 24 children in each group (hospital and home-based) were calculated from the assumptions of weight gain, time to achieve WH >80%, and reduction in cost of treatment respectively.

The formula used for calculating sample size is:

$$\frac{2 (SD)^2}{WD^2} \times \text{factor for } \alpha, \beta$$

where, SD is the standard deviation, WD is the worthwhile difference, power of detection is 90%, and type I error is 0.05. Taking the greatest of the three calculated sample sizes and allowing for 20% dropouts (refusal to continue, unexpected migration of the family to an outlying area, or later diagnosed to have tuberculosis), a sample size of 75 children in each group has been estimated.

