## Data Analysis

Describe plans for data analysis. Indicate whether data will be analyzed by the investigators themselves or by other professionals. Specify what statistical softwares packages will be used and if the study is blinded, when the code will be opened. For clinical trials, indicate if interim data analysis will be required to monitor further progress of the study. (TYPE WITHIN THE PROVIDED SPACE).

Data will be analyzed using the SPSS Windows software. The Epi Info software will be used to calculate anthropometric indices. Enrollment characteristics will be compared between the three treatment groups. The outcome variables will be compared both within and between groups from enrollment to discharge. For normally distributed quantitative variables, means will be compared by ANOVA. Variables not normally distributed will be log transformed before analysis. Categorical variables will be compared by Chi-square test, multiple or logistic regression will be performed to minimise bias if required.

Results from all randomized children will be included in the analysis of the study. Data from children withdrawn because of failure to respond, TB, or voluntary dropout will be included in the analysis upto the time of withdrawal. A supplementary analysis excluding the children withdrawn may also be made.

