#### **Reviewer 3**

Has supported the application with qualification.

Point 1: Since exact age determination is almost impossible, anthropometric indices including weight-for-age and height-for-age will be calculated using estimated ages. SD score is useful if the subject population has a wide age range; the range being 6 months to 5 years in this study. We have kept percentage of median (ie, weight-for-height 70%) as one of the criteria for severe malnutrition in this study because this criterion, rather than SD score, is routinely used at the CRSC. However, SD scores for the 3 anthropometric indices will also be calculated.

Point 2: Definition and specific criteria for resolution of acute illnesses are outlined in the section *Management of acute illness* (page 9).

Point 3: Acuteness of an illness lasts as long as any of the features of the acute illness are present (outlined in the section *Management of acute illness*, page 9). In our previous study (ref 9), the median period of acute illness was 4.5 days (n=627 children).

Point 4: We agree with the reviewer's opinion.

Point 5: Skin fold thickness is very difficult to measure in field situations. It is not routinely practiced in the CRSC. The following instruments will be used for anthropometry:

For weight	Salter scale
For length	Length board with graduations at millimetre level
For MUAC	TALC tape

Point 6: Agree. Would help in ascertaining whether the groups are comparable or not at randomization.

Point 7: Continuous test weighing being difficult and labour-intensive, recording breast milk intake is not feasible. Since the study children will be severely malnourished and more than six months of age, they are likely to be on no or scanty breast milk.

Point 8: The recently published WHO guidelines are conceptually identical to the management guidelines in practice at the CRSC, although there are certain differences (ref 9). Micronutrients will be supplemented separately, as practiced routinely at the CRSC.

Point 9: There is no need for an end-point hemoglobin measurement.

Point 10: The food intake in group C will continue to be quantified till discharge from the NRU on achieving oedema-free weight-for-height 80%. The advice to be rendered to the mothers on discharge has been elaborated on page 12 (paragraphs 1 and 3). This will include advice regarding the approximate amounts of food to be given to the child, and education on health and nutrition.

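### Growth is compared from enrolment to discharge, a window that differs between arms, so neither reading of discharge gives a valid growth comparison

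*Protocol*

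**What the plan says.** Growth is named as an outcome in its own right, beside rate of weight gain and time to recovery. Specific Aim 2 lists "the outcome, including growth, rate of weight gain, speed of loss of oedema". The Project Summary has "Outcome measures that will be used in comparing the three treatments will include growth, time to recovery", and the abstract for the Ethical Review Committee gives the same list. None of them defines growth, and the Outcome Measures list leaves it out. That list asks for follow-up periods of equal length for morbidity and for nothing else.

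Data Analysis fixes the window: "The outcome variables will be compared both within and between groups from enrollment to discharge". The response to Reviewer 3, Point 1, says of weight-for-age, height-for-age and weight-for-height: "However, SD scores for the 3 anthropometric indices will also be calculated".

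Rehabilitation ends at the same threshold in each arm (a percentage of the NCHS median):

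- A: "a health worker will visit the child every week for one month and then at fortnightly intervals until the child achieves an oedema-free WH >80".
- B: "advised to attend the NFU every week for one month and then at fortnightly intervals until they achieve an oedema-free WH >80".
- C: "Children on treatment C will remain admitted in the NRU until they have achieved an oedema-free WH >80".

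The word *discharge*, however, marks different events. In A and B it is departure from the NRU after 7 days (Project Summary, Treatment A, Treatment B, Ethical Assurance). In C it is the point at which the WH target is met.

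**The concern.** A growth comparison needs the same length of observation in each arm, or a model that accounts for time. Here the end of the window is either a growth threshold or a milestone that differs by arm. In the first case the stopping rule largely fixes attained WH, and absolute gains in length reflect how long the child took to recover. In the second, one arm is measured after a week and the other after about three weeks. A statement at the end of the trial that children in one setting grew as well as, or better than, those in another could then come from the window and not from the care. Growth is named in the trial's only comparative aim, so the result would be expected and reported.

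**Working it through.** **Inputs from the protocol.** Sample Size gives hospital time to WH above 80% of 22.5 days (SD 6.2) and weight gain of 8.4 (SD 7.3) g/kg/day. For home-based care with outpatient follow-up it assumes weight gain of 4 g/kg/day and that it "will require approximately 35 days to achieve WH >80"%. It gives no time for arm A. The stay before discharge in A and B is 7 days.

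**The plan's own figures.** No figure is stated for growth. With the protocol's formula and a two-sided 5% level, weight gain gives 2 × 7.3² / 4.4² × 10.507 = 57.8, that is 58 per group, as stated. Dividing by 0.80 for dropout gives 72.5, so 73, close to the stated 75. The stated 15 for time to target is not reproduced: 2 × 6.2² / 12.5² × 10.507 = 5.2, that is 6. It does not drive the total, and the 35 days is taken below as written.

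**Reading 1: discharge means reaching oedema-free WH above 80%.**

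- Elapsed time: 35 − 22.5 = 12.5 days longer in B; 35 / 22.5 = 1.56.
- Length gain is velocity × days. The documents give no linear velocity, so a range is assumed (month of 30.4 days):

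| Assumed velocity, equal in both arms | C, 22.5 days | B, 35 days | Excess in B |
|---|---|---|---|
| 0.5 cm/month | 0.37 cm | 0.58 cm | 0.21 cm |
| 1.0 cm/month | 0.74 cm | 1.15 cm | 0.41 cm |
| 1.5 cm/month | 1.11 cm | 1.73 cm | 0.62 cm |

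- Break-even: B shows no excess once its velocity is 22.5 / 35 = 64% of C's or lower.
- Attained WH: a simulation assumed entry WH spread evenly over 62–70%, linear gain, and the protocol's expected recovery times (SD 6.2 days in both arms). WH at the first measurement above 80% averaged 80.3% in C with daily weighing. In B it averaged 82.4% on the weekly-then-fortnightly schedule and 80.2% if B were also weighed daily. The 2-point gap is overshoot between visits, not a treatment effect.

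**Reading 2: discharge means leaving the NRU at day 7 in A and B, and reaching the target in C.**

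- Windows: 7 against 22.5 days; 22.5 / 7 = 3.2 times longer in C.
- WH at day 7, even at the hospital pace: from 67%, 67 + 13 × 7/22.5 = 71.0%; from 70%, 70 + 10 × 7/22.5 = 73.1%. C is above 80% by rule.
- At the same assumed velocities, C gains 0.25, 0.51 or 0.76 cm more length, from 15.5 extra days.

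**Can a common day be met on the existing schedule?**

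- A and B: visits at days 14, 21, 28 and 35 (7 + 7k). A child who recovers at day 14 or 21 moves to monthly visits, next seen at about day 44 or 51.
- C: the first visit to the nutritional follow-up clinic (NFU) averages 22.5 + 14 = 36.5 days. If recovery time is normal with SD 6.2, 36% of these visits fall within 3 days of day 35 (days 32–38) and 73% within 7 days (days 28–42).
- Of the rest of C, about 19% recover after day 28 and are still in the NRU at day 28. About 9% recover before day 14, and their second two-weekly visit (recovery + 28) falls by day 42. On paper, then, a window of 7 days either way holds a contact for every C child. However, the protocol does not state that length is measured at C's contacts.

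**The case against.** The strongest reply is that the protocol never commits to the comparisons at fault. The Outcome Measures list omits growth, attained WH and length gain are not named as endpoints, and the SD scores are promised in answer to a comment about defining malnutrition and determining age. On that view only a definition is missing, and a statistical analysis plan could supply it. This holds in part: the definition could sit there. The window is different. Data Analysis fixes it for the outcome variables, and the aims and both summaries make growth one of them. A later definition would inherit a window that does not work.

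Several stronger readings are tempting and are not supported:

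- **Attained WH is equal by design.** This is only approximate, holds only under Reading 1, and applies only to recovered children. Withdrawn children are analysed up to withdrawal and may end below target, oedematous children may enter above 70%, and visit spacing allows overshoot.
- **The bias favours home care.** That needs Reading 1. Reading 2 reverses it.
- **Height-for-age rises with time.** The score is age-standardised. A child growing at the reference rate shows no change however long observed, and one growing more slowly falls further over a longer window.
- **There is a spurious 56% excess in length.** That figure needs equal linear velocity, which the documents do not give. The protocol assumes slower weight gain at home.

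Follow-up towards WH above 90% is planned after the target is reached. It could supply later data, but at no common time and outside the stated window.

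**Conclusion.** The concern stands in this form: the protocol compares growth over a window that is not common to the arms, and neither meaning of discharge gives a valid comparison. Under one, attained WH among recovered children is pinned just above 80% and B has about 1.56 times C's observation time. Under the other, C has about 3.2 times that of A and B. The direction of bias cannot be stated until discharge is defined.

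The sizes rest on the protocol's planning times. The length figures rest also on assumed velocities and come to roughly 0.2 to 0.8 cm across both readings.

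A reader might infer that the main results are compromised too. They are not equalised by the stopping rule: weight gain is expressed per day, and time to recovery is itself the measure. The point is worth correcting because growth is an aim-level outcome, but it does not undermine the sample size, which rests on weight gain, time and cost.

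**What to change.** Change the analysis wording only; the clinical discharge rules stay as they are.

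1. In Outcome Measures, add growth, defined as change in weight, length or height, and the three SD scores from randomization to a common time in all randomized children, whether or not they have recovered.
2. In Outcome Measures and Data Analysis, replace *discharge* as an analysis end point with one end point defined identically for all arms. The end point of the weight-gain rate, now the discharge weight, needs the same definition.
3. In Data Analysis, compare growth at that common time, adjusted for the enrolment value, and do not compare attained WH at discharge between arms.
4. For the common time, use about day 35 with a window of roughly 7 days either way; 3 days would miss most first NFU visits in C. Alternatively, fit a repeated-measures model on time since randomization to the scheduled NRU, home and NFU measurements.

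The cost is wording plus, for some children, one added weight and length measurement: A and B children who recover early and move to monthly visits, and C children whose contact in the window would not otherwise include length. Under the model option, these children rely on the model instead. Postponed discharges will shift some A and B visits. NFU attendance is only advised, and the Background describes past follow-up as poor, so some measurements will be missing, possibly unevenly between arms.
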